10.6 Biological Specimens and Data

Study data are protected by the use of a SID number, which is a number specific to the participant. The Investigator is in control of the information that is needed to connect a study sample to a participant; a participant may withdraw consent at any time by notifying the Investigator. If consent is withdrawn, any samples collected prior to that time may still be given to and used by the Sponsor, but no new data or samples will be collected unless specifically required to monitor the safety of the participant.

Leftover samples stored for future research with participant consent will be labeled with a sample identification number. If the participant consents to have his/her samples used for future research, this additional research may not start immediately and may start at any time during the storage period. The participant's sample(s) will be stored by the Sponsor with similar samples in a secure laboratory. The participant's samples will not be kept for more than 25 years after the end of the study in which they were collected. If the participant chooses not to allow his/her study samples to be used for future research, the samples will be destroyed by the Sponsor once they are no longer required for the main study. If future use consent is withdrawn, the Sponsor and the Investigator will ensure that the participant's sample(s) are destroyed unless the identification number has been removed and the participant can no longer be linked to any samples. However, if the participant's sample has already been used for research, the Sponsor is not required to destroy the results of this research. In this case, only the remaining sample(s) will be destroyed.

11 OVERSIGHT

11.1 Safety Data Monitoring Committee

The external, independent SDMC is responsible for safeguarding the interests of study participants via review of accumulating safety data and for supporting study integrity and interpretability based on their review of ongoing study conduct. The SDMC will provide Viela Bio with recommendations for actions with respect to study conduct and the management of participants treated under the study protocol. The SDMC members are independent of Viela Bio and any CRO/organization collaborating with Viela Bio on the study.

The SDMC will not be charged with any formal interim analysis, will not conduct a futility analysis, and will not be asked to consider early study completion for efficacy. For additional details, refer to the SDMC Charter.

11.2 Quality Control and Assurance

To ensure compliance with GCP and all applicable regulatory requirements, the Sponsor may conduct a quality assurance audit. See Section 11.4 for details regarding the audit process.

11.3 Monitoring

The Sponsor and any third party to whom aspects of study management or monitoring have been delegated, will undertake their roles in accordance with all applicable regulations and ICH E6(R2).

A representative of the Sponsor and/or its designee will perform periodic monitoring of the study to ensure compliance with ICH GCP guidelines and regulatory requirements. The Sponsor's designated representatives (the Study Monitors) will inspect the site's study documentation (including qualification and training of site personnel, IRB communications, etc), study data, participants' original medical records, and completed eCRFs. The Investigator agrees to allow unblinded Study Monitors to inspect the drug storage area, IP stocks, drug accountability records, subject charts, original study source documents (regardless of media), and other records relative to study conduct. The Study Monitors will maintain frequent contact with the investigational site and meet with the Investigator and site staff throughout the course of the study.

The Investigator will facilitate monitoring activities and the Study Monitors' access to required records.

During scheduled monitoring visits, the Investigator and the investigational site staff must be available to meet with the Study Monitor in order to discuss the progress of the study, make necessary corrections to eCRF entries, respond to data clarification requests, and respond to any other study-related inquiries from the Study Monitor.

11.4 Audits/Inspections

To ensure compliance with GCP and all applicable regulatory requirements, the Sponsor or its authorized representatives may conduct a quality assurance audit. Local or foreign regulatory authorities may conduct regulatory inspections. Regulatory inspections may be in response to a marketing application, and this may occur years after completion of the clinical study.

Authorized representatives of the Sponsor, a regulatory authority, an IEC, and/or an IRB may visit the site to perform audits or inspections, including review of original medical records. The purpose of a Sponsor audit or regulatory inspection is to systematically and independently examine all study-related activities and documents to determine whether these activities were conducted and data were recorded, analyzed, and accurately reported according to the protocol, ICH GCP guidelines, and any applicable regulatory requirements.

Initial IRB/IEC approval, and all materials approved by the IRB/IEC for this study, including the ICF and recruitment materials, must be maintained by the Investigator and made available for inspection.

In addition to the above, representatives of the Sponsor auditing staff or government inspectors may review the conduct/results of the study at the investigational site. The Investigator should contact the Sponsor immediately if contacted by a regulatory agency about an inspection. The Investigator cooperates with the auditor(s), makes available to the auditor all requested documentation, and ensures that issues detected during these audits are satisfactorily resolved. The Investigator supplies the Sponsor with copies of all documentation and correspondence related to regulatory agency audits as outlined in the Clinical Trial Agreement. If the results of the audit result in a Form FDA 483 (or similar document from another regulatory agency), the Investigator promptly provides a copy to a Sponsor representative and a draft response to the Sponsor prior to submission to the regulatory agency.

11.4.1 Records

11.4.2 Data Capture and Management

Clinical Data Management (CDM) will be performed according to the Data Management Plan (DMP). The DMP will document procedures and roles and responsibilities related to CDM activities, including data validation, data transfer and reconciliation, CDM communications, medical coding and dictionaries, CDM reports, and data formats. An electronic data capture system compliant with 21 Code of Federal Regulations Part 11 will be used for data collection and query handling. The Investigator will ensure that data are recorded in the eCRFs as specified in the study protocol and in accordance with the eCRF Completion Guidelines provided. The Investigator ensures the accuracy, completeness, and timeliness of the data recorded and of the provision of answers to data queries. The Investigator will sign the completed eCRFs electronically. Upon completion of the study, a copy of the completed eCRFs will be provided to the study site for archival purposes.

11.4.3 Source Documentation

The Investigator is responsible for maintaining adequate and accurate medical records from which the Investigator/designee will transcribe information in the eCRFs.

11.4.4 Records Retention

Essential documents should be retained until at least 2 years after the last approval of a marketing application in an ICH region and until there are no pending or contemplated marketing applications in an ICH region or at least 2 years have elapsed since the formal discontinuation of

clinical development of the IP. These documents should be retained for a longer period, however, if required by applicable regulatory requirement.

The Investigator may not destroy any study records without written permission from the Sponsor.

12 PUBLICATION POLICY

The publication policy of the Sponsor is discussed in the Investigator's Clinical Research Agreement.

13 FINANCING AND INSURANCE

Financing and insurance for this study will be addressed in the Clinical Trial Agreement with the study site(s).

15 APPENDICES

APPENDIX 1 NATIONAL INSTITUTE OF ALLERGY AND INFECTIOUS DISEASE AND FOOD AND ALLERGY ANAPHYLAXIS NETWORK GUIDANCE FOR ANAPHYLAXIS DIAGNOSIS

National Institute of Allergy and Infectious Disease (NIAID) and Food and Allergy Anaphylaxis Network (FAAN) define anaphylaxis as a serious allergic reaction that is rapid in onset and may cause death (Sampson et al, 2006). They recognize 3 categories of anaphylaxis, with criteria designated to capture from 80% of cases (Category 1) to > 95% of all cases of anaphylaxis (for all 3 categories).

- 1. Acute onset of an illness (minutes to several hours) with involvement of the skin, mucosal tissue, or both (eg, generalized hives, pruritus or flushing, swollen lips-tongue-uvula), AND AT LEAST ONE OF THE FOLLOWING:
 - a. Respiratory compromise (eg, dyspnea, wheeze-bronchospasm, stridor, reduced peak expiratory function [PEF], hypoxemia).
 - b. Reduced blood pressure or associated symptoms of end-organ dysfunction (eg, hypotonia [collapse], syncope, incontinence).
- 2. Two or more of the following that occur rapidly after exposure to a likely allergen for that patient (minutes to several hours):
 - a. Involvement of the skin-mucosal tissue (eg, generalized hives, itch-flush, swollen lips-tongue-uvula).
 - b. Respiratory compromise (eg, dyspnea, wheeze-bronchospasm, stridor, reduced PEF, hypoxemia).
 - c. Reduced blood pressure or associated symptoms (eg, hypotonia [collapse], syncope, incontinence).
 - d. Persistent gastrointestinal symptoms (eg, crampy abdominal pain, vomiting).
- 3. Reduced blood pressure after exposure to known allergen for that patient (minutes to several hours):
 - a. Infants and children low systolic blood pressure (age specific) or greater than 30% decrease in systolic blood pressure.
 - b. Adults systolic blood pressure of less than 90 mmHg or greater than 30% decrease from that participant's baseline.

APPENDIX 2 2019 EUROPEAN LEAGUE AGAINST RHEUMATISM/AMERICAN COLLEGE OF RHEUMATOLOGY CLASSIFICATION SYSTEM FOR SYSTEMIC LUPUS ERYTHEMATOSUS

Entry criterion

Antinuclear antibodies (ANA) at a titer of ≥1:80 on HEp-2 cells or an equivalent positive test (ever)

If absent, do not classify as SLE If present, apply additive criteria

Additive criteria

Do not count a criterion if there is a more likely explanation than SLE. Occurrence of a criterion on at least one occasion is sufficient. SLE classification requires at least one clinical criterion and ≥10 points. Criteria need not occur simultaneously.

Within each domain, only the highest weighted criterion is counted toward the total score§.

Clinical domains and criteria	Weight	Immunology domains and criteria	Weight
Constitutional		Antiphospholipid antibodies	
Fever	2	Anti-cardiolipin antibodies OR	
Hematologic		Anti-β2GP1 antibodies OR	
Leukopenia	3	Lupus anticoagulant	2
Thrombocytopenia	4	Complement proteins	
Autoimmune hemolysis	4	Low C3 OR low C4	3
Neuropsychiatric		Low C3 AND low C4	4
Delirium	2	SLE-specific antibodies	
Psychosis	3	Anti-dsDNA antibody* OR	
Seizure	5	Anti-Smith antibody	6
Mucocutaneous			
Non-scarring alopecia	2		
Oral ulcers	2		
Subacute cutaneous OR discoid lupus	4		
Acute cutaneous lupus	6		
Serosal			
Pleural or pericardial effusion	5		
Acute pericarditis	6		
Musculoskeletal			
Joint involvement	6		
Renal			
Proteinuria >0.5g/24h	4		
5 117 61 11 171	8		
Renal biopsy Class II or V lupus nephritis	10		

Classify as Systemic Lupus Erythematosus with a score of 10 or more if entry criterion fulfilled.

Source: Aringer et al, 2019.

β2GP1: β2-glycoprotein 1; C: complement; dsDNA: double-stranded DNA; Hep-2: human epithelial type 2 cells;

SLE: systemic lupus erythematosus.

APPENDIX 3 STUDY-SPECIFIED OPPORTUNISTIC INFECTIONS THAT MEET EXCLUSION CRITERIA

CMV: cytomegalovirus; EBV: Epstein-Barr virus; HBV: hepatitis B virus; HCV: hepatitis C virus; TB: tuberculosis.

Source: Winthrop et al, 2015.

^a Generally does not occur in the absence of immunosuppression, but whose presence indicates a potential or likely alteration in host immunity.

^b Can occur in patients without recognized forms of immunosuppression, but whose presence indicates a potential or likely alteration in host immunity.

^c Published data are currently lacking, but expert opinion believes that risk is likely elevated in the setting of biologic therapy.

APPENDIX 4 PREDISONE EQUIVALENT OF ORAL GLUCOCORTICOID DOSE

Glucocorticoid	Prednisone Equivalent Dose						
PO prednisone	5 mg	7.5 mg	10 mg	20 mg	30 mg	40 mg	
Prednisolone	5 mg	7.5 mg	10 mg	20 mg	30 mg	40 mg	
Methylprednisolone	4 mg	6 mg	8 mg	16 mg	24 mg	32 mg	
Hydrocortisone	20 mg	30 mg	40 mg	80 mg	120 mg	160 mg	
Cortisone	25 mg	37.5 mg	50 mg	100 mg	150 mg	200 mg	
Triamcinolone	4 mg	6 mg	8 mg	16 mg	24 mg	32 mg	

PO: oral(ly).

APPENDIX 5 ORAL GLUCOCORTICOID TAPERING SCHEDULE

Visit	Dose of Oral Prednisone or Equivalent at Start of Specified Study Visit ^a						
Week 0	Investigators may initiate OGC taper as tolerated; target ≤ 7.5 mg/day to meet response criteria ^b						
Week 4	40 mg	30 mg	20 mg	10 mg	7.5 mg		
Week 8	30 mg	22.5 mg	15 mg	7.5 mg	5 mg ^c		
Week 12	20 mg	15 mg	10 mg	7.5 mg	5 mg ^c		
Week 16	12.5 mg	10 mg	7.5 mg	5 mg ^c	≤5 mg °		
Week 20	7.5 mg	7.5 mg	7.5 mg	≤5 mg ^c	≤ 5 mg °		
No Change in OGC Permitted between Week 20 and Week 24							
Week 24 to Week 36	It is encouraged to taper OGC dose beyond the target for response criteria of 7.5 mg/day including discontinuation of OGC up to Week 36, if clinically feasible.						
No change in OGC is permitted between Week 36 and Week 48.							

OGC: oral glucocorticoid.

The doses in the table are shown for prednisone. Refer to Table 3 for equivalent doses of other OGCs.

The OGC tapering schedule represents an example of a tapering regimen to provide guidance to Investigators in the approach to mandatory steroid taper starting at Week 4 with a target OGC dose of ≤ 7.5mg/day prednisone (or equivalent) to meet the response criteria at Week 20 and to aim for a lower daily dose at Week 36.

^a Specified prednisone dose is dose at the beginning of the week.

^b Due to variability in participant responses to OGC treatment and tolerability of taper, Investigators have flexibility in how the OGC dose is reduced at each study visit.

c Investigators are encouraged to taper OGC dose beyond the target for response criteria of ≤ 7.5 mg/day including discontinuation of OGC, if clinically feasible.

# LIST OF ABBREVIATIONS

Abbreviation or Specialized Term	Definition
AE	adverse event
AESI	adverse event of special interest
ANCOVA	Analysis of covariance
AUC	area under the concentration-time curve
BICLA	BILAG 2004 Index-Based Combined Lupus Assessment
BILAG	British Isles Lupus Assessment Group
CI	confidence interval
CLASI	Cutaneous Lupus Erythematosus Disease Area and Severity Index
CLASI-A	Cutaneous Lupus Erythematosus Disease Area and Severity Index- Activity
CNS	central nervous system
ECG	electrocardiogram
GC	glucocorticoid
HRQoL	health related quality of life
IP DG	Investigational product
PGA	physician global assessment of disease activity
LLDAS	Lupus Low Disease Activity State
LLN	lower limit of normal
LOCF	last observation carried forward
mCLASI-A	modified CLASI-A
MCP	metacarpophalangeal
MDA	minimal disease activity
MedDRA	Medical Dictionary for Regulatory Activities
MMRM	mixed model for repeated measures
OGC	oral glucocorticoid

Abbreviation or Specialized Term	Definition
PD	pharmacodynamic(s)
pDC	plasmacytoid DC
РК	Pharmacokinetic(s)
PIP	proximal interphalangeal
РТ	preferred term
Q12W	every 12 weeks
QTc	corrected QT interval
RF	rheumatoid factor
SAE	serious adverse event
SC	subcutaneous(ly)
SE	standard error
SLE	systemic lupus erythematosus
SLEDAI-2K	SLE Disease Activity Index 2000
SLEDAI-2KG	SLEDAI-2K GC
SOC	system organ class
SPP	statistical programming plan
SRI	SLE Responder Index
TEAE	treatment-emergent adverse event
TESAE	treatment-emergent serious adverse event
ULN	upper limit of normal
UPCR	urine protein:creatinine ratio
VAS	visual analog scale

This document describes the statistical analysis for protocol VIB7734.P2.S1, a Phase 2, multicenter, international, randomized, double-blind, placebo-controlled, parallel-arm trial to assess the efficacy and safety of VIB7734 in participants with moderate to severely active systemic lupus erythematosus (SLE).

# 2 STUDY OVERVIEW

## 2.1 Study Objectives and Endpoints

The objectives and corresponding endpoints are listed in Table 1 below:

Table 1Study Objectives and Endpoints

Primary objective	Endpoints/variables
To evaluate the effect of VIB7734 compared to placebo in reducing SLE disease activity at Week 48 in participants treated with standard of care therapy	Proportion of participants achieving a BILAG-2004 Index-based BICLA response and an OGC dose $\leq 7.5$ mg/day and $\leq$ Baseline (Day 1) dose of prednisone or equivalent at Week 48.
	The BICLA response is defined as meeting all the following conditions as compared to Baseline:
	
 
BILAG-2004 Index improvement (all Baseline [Day 1] BILAG A improving to B/C/D, all Baseline [Day 1] BILAG B to C/D, and ≤ 1 new BILAG B and no new BILAG A.
 

	• No deterioration in SLEDAI-2K total score.
	• No significant worsening in PGA score (<10% increase (< 0.3-point increase on a 3-point VAS)).
	• No use of restricted medications beyond the protocol-allowed threshold before assessment.
	• No discontinuation of IP.
Secondary objectives	Endpoints/variables
To evaluate the effect of VIB7734 compared with placebo to reduce cutaneous disease activity at Week 12.	Proportion of participants with CLASI-A score $\geq 10$ at Baseline who achieve $\geq 50\%$ reduction from Baseline in CLASI-A score at Week 12. Reduction of 50% in CLASI-A score is defined by meeting all the following conditions:
	• A ≥ 50% reduction of CLASI-A score at Week 12 as compared to Baseline.
	• No use of restricted medications beyond the protocol-allowed threshold before assessment.
	• No discontinuation of IP.
To evaluate the effect of VIB7734 compared with placebo to reduce SLE disease activity at Week 48.	Proportion of participants achieving a SRI-4 response and an OGC dose $\leq$ 7.5 mg/day and $\leq$ Baseline (Day 1) dose of prednisone or equivalent at Week 48. The SRI-4 response is defined as meeting all of the following conditions compared to Baseline:

Tuste I Study Objectites und Endpo	
	• Reduction from Baseline of ≥ 4 points in the SLEDAI-2K.
	• No new organ system affected as defined by 1 or more BILAG A or 2 or more BILAG B items.
	• No significant worsening in PGA score (<10% increase (< 0.3 point increase on a 3-point VAS)).
	• No use of restricted medications beyond the protocol-allowed threshold before assessment.
	• No discontinuation of IP.
To evaluate the effect of VIB7734 compared with placebo on sustained OGC reduction from Week 36	Proportion of participants with OGC dose $\geq 10 \text{ mg}$ prednisone or equivalent at Baseline (Day 1) who:
to Week 48.	• Achieve OGC dose ≤ 7.5 mg/day prednisone or equivalent at Week 36.
	• Maintain OGC dose ≤ 7.5 mg/day from Week 36 through Week 48.
	• No use of restricted medications beyond the protocol-allowed threshold before assessment.
	• No discontinuation of IP.
To evaluate the effect of VIB7734 compared with placebo to achieve low disease activity at Week 48.	Proportion of participants achieving LLDAS at Week 48. LLDAS is defined as meeting all the following conditions:
	• SLEDAI-2K ≤ 4, with no activity in major organ system (renal, CNS, cardiopulmonary, vasculitis, fever) and hemolytic anemia or gastrointestinal activity.
	• No new lupus disease activity as compared to the previous assessment.
	• $PGA \le 1$ (on a 3-point VAS).
	
 
Current prednisone or equivalent dose of ≤ 7.5 mg/day.
 

	• Well-tolerated standard maintenance doses of immunosuppressive drugs and approved treatments as allowed and specified in the protocol.
	• No use of restricted medications beyond the protocol-allowed threshold.
	• No discontinuation of IP.
Safety objective	Endpoints/variables
To evaluate the safety and tolerability of VIB7734.	Incidence of adverse events, serious adverse events, and adverse events of special interest.
PK/PD/Immunogenicity Objectives	Outcome Measures
To characterize the PK, PD, and immunogenicity of VIB7734.	VIB7734 concentrations, change in pDC,

# Table 1Study Objectives and Endpoints

Exploratory objectives	Endpoints/variables

### Table 1Study Objectives and Endpoints

#### 2.2 Study Design

This study is a Phase 2, multicenter, international, double-blind, randomized, placebocontrolled, parallel-arm trial to assess the efficacy and safety of VIB7734 in participants with moderate to severely active SLE.

[figure not shown]
In this study, approximately 195 participants will be randomized in a ratio of 1:1:1 (65 participants per group) to receive VIB7734 200 mg every 4 weeks subcutaneously (SC), VIB7734 200 mg every 12 weeks (Q12W) SC, with an additional 200 mg SC dose at Week 4, or placebo. To maintain blinding, participants randomized to the VIB7734 200 mg Q12W SC dosing regimen will receive SC placebo injections on dosing visits outside the Q12W schedule. Randomization will be stratified by SLEDAI-2K total score at Screening

 $(\geq 10 \text{ or } < 10)$  and prednisone or equivalent oral glucocorticoid (OGC) dose at Baseline (Day 1) ( $\geq 10 \text{ mg or } < 10 \text{ mg}$ ).

The study will comprise a Screening period of approximately 4 weeks (Days -28 to -1), Randomization on Day 1, treatment and assessments through Week 48, and a Safety Follow-Up period of 8 weeks (through Week 56).

A study schematic is presented in Figure 1.

### Figure 1 Study Flow Diagram

\*Two Week extension under exceptional consideration (delayed labs, drug wash out, COVID-19-related delays) with Medical Monitor approval.

## 2.3 Sample Size

The sample size was calculated based on the primary efficacy outcome measure. Assuming a placebo response rate of 20%, 65 participants per treatment group will provide at least 80% power to detect an increase in response of 20% in a VIB7734 group as compared to the placebo group at the 2-sided alpha level of 0.10 using a Chi-square test. The minimum detectable difference is 13% between placebo and VIB7734 treatment groups. The assumption of a 20% responder rate for placebo is based upon published results (Furie R et al, 2017).

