9.3 Determination of Sample Size

The sample size was calculated based on the primary efficacy outcome measure. Assuming a placebo response rate of 20%, 65 participants per treatment group will provide at least 80% power to detect an increase in response of 20% in a VIB7734 group as compared to the placebo group at the 2-sided alpha level of 0.10 using a Chi-square test. The minimum detectable difference is 13% between the 2 treatment groups. The assumption of a 20% responder rate for placebo is based upon published results (Furie et al, 2017).

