#### 3.7 Efficacy Analyses

#### **3.7.1 Primary Endpoint and Analyses**

#### 3.7.1.1 Primary endpoint and estimand

The estimand of primary interest is defined as follows, using composite variable strategy to address intercurrent events.

- Population: Participants in the full analysis set with active SLE despite receiving 1 or more standard of care treatments as defined by the inclusion-exclusion criteria of the study (excluding subjects from Russia and Ukraine sites)
- Variable (endpoint): Response in BICLA + OGC ≤ 7.5 mg/day and ≤ Day 1 dose at Week 48, where BICLA is defined by meeting the following criteria compared to Baseline:
  - BILAG-2004 Index improvement (all Baseline BILAG A improving to B/C/D, all Baseline BILAG B to C/D, and ≤ 1 new BILAG B and no new BILAG A).
  - No deterioration in SLEDAI-2K total score, where deterioration is defined as an increase from baseline of > 0 points in SLEDAI-2K.
  - No significant worsening in PGA score (< 0.3 point increase).

  - No use of restricted medications beyond the protocol-allowed threshold (see section 3.6) before assessment.
  - No discontinuation of IP.
- Intercurrent event:
  - Rescue medications: Captured in the primary variable definition.
  - Treatment discontinuation: Captured in the primary variable definition.
- Population-level summary: Difference in proportions of responders between the VIB7734 group and placebo group.

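### The SAP's 80% power is for 65 analysed per group, but its primary estimand leaves out Russia and Ukraine participants and the power is not restated for the smaller population

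*SAP*

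**What the plan says.** SAP 2.3 repeats the calculation in Protocol 9.3. Its central statement is that "65 participants per treatment group will provide at least 80% power to detect an increase in response of 20% in a VIB7734 group". The other inputs are 20% response on placebo and a chi-square test at two-sided alpha 0.10. The section also gives a detectable difference: "The minimum detectable difference is 13% between placebo and VIB7734 treatment groups". SAP 2.2 makes clear that 65 is the number randomized: "approximately 195 participants will be randomized in a ratio of 1:1:1 (65 participants per group").

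SAP 3.7.1.1 then defines the primary estimand population as the full analysis set, "excluding subjects from Russia and Ukraine sites". SAP 3.7.2.1 applies the same exclusion to every secondary population. The primary estimand in Protocol 9.5.1 has no country exclusion.

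Two other SAP sections do not carry the exclusion. SAP 3.3.2 defines the full analysis set as everyone randomized and dosed, and SAP 3.7.1.2 runs the primary comparison on that set.

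Nothing stated offsets the loss. Protocol 5.4 allows replacement only of participants who were randomized but not dosed. SAP 3.7.1.4 keeps early discontinuations in the denominator as nonresponders, but a country exclusion takes participants out of the denominator altogether.

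**The concern.** The power statement was written for the protocol's population, and the SAP has since narrowed the population of its primary estimand. SAP 2.3 was not revisited, so a reader will attach 80% power to an analysis that may include fewer than 65 per arm. The design has one spare participant per arm over the 64 that the planning formula requires, so there is little room to absorb any exclusion.

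What is at stake is how the result is read. If the primary comparison is not significant, it would be judged against 80% power when the analysed population may have had less. The two descriptions of the population add a second problem: the 80% matches one of them and not the other.

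**Working it through.** **Inputs.** From SAP 2.3: p0 = 0.20, p1 = 0.40, two-sided alpha 0.10 (z = 1.645), uncorrected chi-square, one VIB7734 group against placebo. From SAP 2.2: 65 randomized per group. The number excluded per arm is **not given**; I assume loss is even across the arms and show a range.

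**Step 1: reproduce the stated power.** With the pooled variance under the null, p̄ = 0.30:

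power = Φ{ [0.20 − 1.645 × √(2 × 0.30 × 0.70 / n)] / √[(0.20 × 0.80 + 0.40 × 0.60) / n] }

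At n = 65: √(0.42/65) = 0.0804, times 1.645 = 0.1322; √(0.40/65) = 0.0784; (0.20 − 0.1322)/0.0784 = 0.864; Φ(0.864) = 80.6%. Exact enumeration of the Pearson test gives 81.2%, and the unpooled formula Φ(0.20/0.0784 − 1.645) gives 81.7%. The stated figure is correct for 65 analysed per arm. The smallest n that reaches 80% by the pooled formula is 64.

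**Step 2: reproduce the minimum detectable difference.** Solve d = 1.645 × √[2p̄(1 − p̄)/n] with p̄ = 0.20 + d/2. At n = 65, d = 12.7 points, which rounds to the stated 13.

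**Step 3: repeat for smaller n per arm.**

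| Analysed per arm | Excluded per arm | Pooled | Exact | Unpooled | Min. detectable difference (points) |
|---|---|---|---|---|---|
| 65 | 0 | 80.6% | 81.2% | 81.7% | 12.7 |
| 64 | 1 | 80.1% | 80.7% | 81.2% | 12.8 |
| 63 | 2 | 79.5% | 79.9% | 80.6% | 12.9 |
| 61 | 4 | 78.4% | 79.0% | 79.5% | 13.2 |
| 60 | 5 | 77.8% | 78.3% | 79.0% | 13.3 |
| 55 | 10 | 74.5% | 75.5% | 75.8% | 13.9 |
| 50 | 15 | 70.9% | 72.0% | 72.3% | 14.7 |

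As a share: 10% excluded leaves 65 × 0.90 = 58.5 per arm and 76.8% pooled power; 20% leaves 52 and 72.4%.

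**Step 4: locate the threshold.** Power drops below 80% at two excluded per arm (2/65, about 3%) by the pooled and exact methods, and at four per arm (4/65, about 6%) by the unpooled formula.

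These figures use the planning test. The planned analysis is a logistic model adjusted for the stratification factors, and uneven exclusion across arms would shift the figures slightly.

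**The case against.** The strongest reply is that SAP 2.3 contains no error. Its sentence is conditional on 65 per group, records how the size was chosen, and reproduces. That stands. Protocol 9.3 is not at fault either, because the protocol has no exclusion.

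A reader might infer that the trial fails to reach 80% power. The documents do not support that. They do not say how many participants, or whether any, were randomized at the excluded sites; enrolment is given only as approximately 195, so over-enrolment is possible although none is stated; and SAP 3.3.2 and 3.7.1.2, read literally, keep these participants in. Small losses also matter little: two per arm costs about one percentage point (80.6% to 79.5%), and whether that crosses 80% depends on the formula. A material fall needs an assumed loss of 10 or more per arm.

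A reader might also infer that the 13% minimum detectable difference is wrong, since from 13 responders out of 65 on placebo the smallest significant gap in whole participants is 9/65 = 13.8 points. That gap reflects whole counts. The usual continuous calculation gives 12.7, so 13 is sound at 65 per arm.

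Finally, SAP 3.7.1.5 describes the trial as exploratory, and SAP 3.7.1.2 reports a 90% interval that shows precision whatever the planning power. This limits the consequence, but it does not make the power statement apply to the population that SAP 3.7.1.1 defines.

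**Conclusion.** The point holds as a mismatch between sections of the SAP. The stated power is right for 65 analysed per arm and is not supported for the primary estimand population, which excludes two countries with no stated replacement, added enrolment or revised calculation. The size of the shortfall cannot be fixed from the documents. Under even loss across arms and the SAP's own planning inputs it runs from negligible (79.5% at 63 per arm) to substantial (70.9% at 50 per arm), pooled. The minimum detectable difference moves less, from 12.7 to 14.7 points over 65 to 50 per arm. The unresolved choice between the restricted and unrestricted full analysis set belongs to the same point, because it decides whether the stated power applies.

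**What to change.** 1. In SAP 2.3, state the number per arm expected in the primary population after the country exclusion, with the power and minimum detectable difference at that number. Keep the 65-per-group figure as the planning basis for all countries.
2. Align SAP 3.3.2 and 3.7.1.2 with 3.7.1.1 so that there is one primary population, named the same way throughout.
3. Pre-specify the same primary model on the all-country full analysis set as a supplementary analysis. The existing one in SAP 3.7.1.3 changes only the handling of intercurrent events.

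The cost is SAP wording, one extra run of an existing model, and a stated power that will look less favourable. No extra patients are needed.
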